11.4.4 Drug Accountability

The investigator and pharmacist are responsible for correct storage of vaccine. The vaccine made available for this clinical trial must be used in accordance with the protocol and must only be handled by the investigator or appropriately designated individuals. Documentation of receipt and disposition of the vaccine will be managed in accordance with study operational procedures. At completion of the trial, or during routine monitoring visits, the PI or his designee will perform a full drug accountability check.

The master record must include:

- Date of receipt of vaccine shipment
- All batch numbers
- Quantities received

The dispensing record must include:

- Quantities dispensed
- Identification of the person to whom vaccine was administered
- Date of each dispensing

These master and dispensing records are separate from records kept for individual trial patients.

Further safety measures were implemented in the latter half of 2019 and the beginning of 2020, resulting from safety events on study. Patients will receive their 1st vaccine in the Oncology Treatment Center (OTC) and will receive a normal saline bolus by IV prior to vaccine administration. The IV saline lock will remain in place during the post-vaccine monitoring period for the purpose of quick administration of additional fluids and/or medication should either be necessary. Supportive medications for post-vaccine reactions may include the following by IV: normal saline bolus, Benadryl, Solu-medrol.

To date (January 10, 2020), we have analyzed immune responses in 16 patients who received vaccine 1 and were batch assayed. We believe that the observed toxicities are related to cytokine release syndrome (CRS). The immune responses across 4 degrees of reactions (ranging from no reactions to Grade III reactions) demonstrate a significant difference between levels of cytokines (G-CSF, GM-CSF, IFN- γ , IL-10, IL-2, IL-8, MIP1- α , and TNF- α) two hours after vaccine, as compared to those levels pre-vaccination, with IL-

6 levels also nearing significance. For these cytokines, subsequent pairwise comparisons included comparisons involving those experiencing Grade III adverse events after Tukey adjustment. These data suggest that the adverse event reactions following PEP-CMV vaccination are indeed immune-related.

The cumulative data indicate that PEP-CMV vaccination is inducing the activation of T cells specific for the target antigen pp65. Furthermore, in patients with AEs, the pp65-specific T cell activation may be inducing a temporary elevation of pro-inflammatory cytokines. We believe that the vaccine reactions we have been observing in PERFORMANCE are likely indicative of vaccine potency. Patients who have demonstrable Grade III reactions also have measurable cellular responses to the PEP-CMV vaccines, which may be indicative of clinical responses.

CRS is associated with elevated circulating levels of cytokines including IL-6 and IFN γ . Commonly referred to as an infusion reaction, it results from the release of cytokines from cells targeted by the antibody, as well as immune effector cells recruited to the area. When cytokines are released into the circulation, systemic symptoms such as fever, nausea, chills, hypotension, tachycardia, asthenia, headache, rash, scratchy throat, and dyspnea can result. In most patients, the symptoms are mild to moderate in severity and are managed easily. However, some patients may experience severe, life-threatening reactions that result from massive release of cytokines. Massive cytokine release is an oncologic emergency, and special precautions must be taken to prevent life-threatening complications. A CRS Management Plan based upon the ASTCT Consensus Grading [113] is provided in [Table 2](#) below for the mitigation of symptoms of CRS. Please note that ASTCT Consensus Grading guidelines refer to the CTCAE v.5 description of constitutional symptoms for its CRS term.

Table 2. CRS Management Plan based upon the ASTCT Consensus Grading

Grade of Toxicity	ASTCT Definition	Management Plan
1	Fever $\geq 38^{\circ}\text{C}$, with or without constitutional symptoms ⁴ , not attributable to another cause	Symptomatic management only
2	Fever $\geq 38^{\circ}\text{C}$ with hypotension not requiring vasopressors and/or hypoxia requiring the use of oxygen delivered by low-flow nasal cannula (≤ 6 L/minute) or blow-by	Hypotension: Clearly establish a baseline blood pressure; if hypotension develops, give fluids. Other reactions: Patients with grade 2 toxicity will be individually tailored, depending on the patient age and medical co-morbidity, and therefore clinical judgement will be crucial prior to use of immunosuppression for grade 2 toxicity. Patients with grade 2 toxicity will be monitored in the OTC with very close cardiac monitoring.

⁴ The associated constitutional symptoms may be reported, but do not affect CRS grade per ASTCT Consensus Grading Guidelines.

3	Fever $\geq 38^{\circ}\text{C}$ with hypotension requiring 1 vasopressor with or without vasopressin and/or hypoxia requiring high-flow nasal cannula ($>6 \text{ L/minute}$), facemask, nonrebreather mask, or venturi mask not attributable to another cause	If grade 3 toxicity develops where fluid resuscitation and 1 low dose vasopressor are not sufficient to reverse the hypotension, the patient will be transferred and monitored closely in the emergency department. All patients with grade 3 toxicity will receive immunosuppressive agents including corticosteroids, such as 2mg/kg Solu-medrol. In severe cases, Tocilizumab, antihuman IL-6R mAb, will be administered. This drug is stocked in the Duke pharmacy.
4	Fever $\geq 38^{\circ}\text{C}$ with hypotension requiring multiple vasopressors (excluding vasopressin) and/or hypoxia requiring positive pressure (e.g., CPAP, bilevel positive airway pressure, intubation, mechanical ventilation) not attributable to another cause	All patients with immediate, life-threatening toxicity will be treated with full support, including mechanical ventilation, immunosuppressive agents, Tocilizumab to prevent inflammatory cascade, and close comprehensive organ monitoring.

11.5.2 Special Consideration

Due to the impact of high dose steroids on the development of an optimal immune response, if a patient demonstrates neurologic or cerebral radiographic signs suggestive of a localized inflammatory reaction, secondary to the immune response triggered by PEP-CMV vaccination, that requires an increase in dexamethasone dose, every effort should be made to not increase the dose above 4 mg per day at any time. Instead, patients should be treated with bevacizumab at the reduced dose of 7.5 mg/kg IV approximately every 3 weeks. If a patient requires planned treatment for their tumor with bevacizumab $> 7.5 \text{ mg/kg}$ approximately every 3 weeks, they will be considered off study and enter the follow-up phase. Neuroimaging (MRI) will be performed according to protocol schedule and, at that time, it will be assessed whether further treatment with bevacizumab is needed to control the cerebral inflammation. Bevacizumab will not be provided by the study. Every attempt should be made to reduce or discontinue dexamethasone, when clinically possible, so as not to mitigate immune response.

If there are AEs or other circumstances prohibiting the use of bevacizumab, corticosteroids, surgery, or other interventions deemed more appropriate for the patient by the treating physician will be used, if needed, to treat any localized inflammatory reaction secondary to DC vaccination.

11.5.3 Allergy Testing

Patients who experience a hypersensitivity reaction as described in Section 15.3 may be offered optional Allergy Testing. To complete the optional Allergy Testing, patients must sign the Allergy Test Consent Form. Allergy testing will only be done on patients who have experienced a hypersensitivity reaction following vaccine administration, in an attempt to uncover which specific element of Component A and/or Component B results in the

reaction. Patients will receive intradermal injections of potential allergens to both the left and the right groin. The allergens include components that are present in Component A and Component B of the PEP-CMV vaccine, as relevant. Each intradermal injection will be administered 1 hour apart and blood draws (~20 mL) will be taken 1 hour prior to the first injection and 1 hour following the final injection. Blood (~20 mL) will be drawn to monitor immune activity through analysis of TNF α , GM-CSF, IFN α , IFN γ , IL-6, and IL-1, as appropriate. Patients will receive SLP and Montanide in the right groin and GM-CSF, gB, and KLH in the left groin. If the patient has only received either Component A or Component B, they will only receive intradermal injections of the elements that were part of the vaccine that they received. Patients will be monitored according to Allergy and Immunology standard of care practices in the clinic.

11.5.4 Unacceptable Toxicities

The original definition of unacceptable toxicities in this study was any vaccine-related or any non-neurologic \geq Grade 3 toxicity of any duration not attributable to TMZ, bevacizumab, and/or disease progression; any Grade 4 toxicity, including neurologic events not due to progressive disease; or any life threatening-event not attributable to concomitant medication, co-morbid event, or disease progression. The definition of unacceptable toxicity was revised with v.20200117 of the protocol and will be defined now as any life-threatening \geq Grade 3 toxicity that is possibly, probably, or definitely related to the PEP-CMV vaccine with the following exceptions (updated in the v.20200504 protocol). A portion of the Grade 3 vaccine reactions noted in prior patient experiences with the PEP-CMV vaccine, described in Sections [11.5.1](#) and [14.2.1](#), will not be considered unacceptable if they are indicative of immune response. That is, toxicities such as Grade 3 flu-like symptoms, fever, and chills/rigors will not be considered unacceptable toxicities if the duration is less than 72 hours. Please see Section [11.5.1](#) for guidelines on management of immune response, including cytokine release syndrome (CRS). Any \geq Grade 3 organ toxicity (cardiac, renal, hepatic), including CRS-related toxicities such as hypotension and tachycardia, of any duration will be considered an unacceptable toxicity. Toxicities will be tracked on all subjects who received PEP-CMV vaccine using the NCI CTCAE (Version 4.03) criteria. Patients who experience unacceptable toxicities will not continue to receive vaccine therapy. Although not considered an unacceptable toxicity, any patient with \geq Grade 2 urticaria will not receive further vaccines, will be withdrawn from the study, and will be replaced if less than 3 vaccines have been administered without unacceptable toxicity.

The prevalence of unacceptable toxicities occurring during the initial 3 bi-weekly vaccinations or the vaccinations administered concurrently with temozolomide will be continuously monitored. If more than 25% of accrued patients experience unacceptable toxicities, then accrual will be suspended and reported toxicity will be carefully reviewed to determine if modifications to the protocol treatment should occur. Peptide vaccinations employing Montanide ISA-51 as adjuvants have generally been well tolerated in human patients in numerous phase I-III trials.

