20200826	Sections 1, 5, 11.1, 11.4.2, 11.5.1, 11.5.2, 11.5.4, 11.5.5, and 16.4	Updated investigators. Definition of unacceptable toxicity revised per FDA request under IND (Sections 1, 11.5.4). New abbreviation added (Section 5). Language added regarding how indeterminate MGMT methylation will be handled (Section 11.1). Updates to safety precautions (Sections 11.1, 11.4.2). Revised CRS Management Plan per FDA request under IND (Section 11.5.1). New section added regarding use of reduced dose of bevacizumab for inflammatory response (Section 11.5.2). CTCAE version clarified as 4.03 (Sections 11.5.4, 11.5.5, 16.4)		

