	
Beginning with protocol version 20181218, patients who are MGMT unmethylated will only receive one adjuvant cycle of the TMZ regimen according to their assigned randomized arm. Patients who are MGMT methylated or whose methylation status is inconclusive will continue with up to 12 cycles of TMZ. All patients enrolled prior to approval of protocol version 20181218 will receive 6-12 cycles of TMZ, independent of their MGMT methylation status. Patients who are dependent on steroid supplements above immune suppressive levels (4 mg) at time of vaccination or who are unable to tolerate TMZ will be withdrawn from the study and replaced before vaccination.
 
Up to 70 patients may be consented on the main informed consent to meet the goal of 26 evaluable patients (13 per arm) for the primary outcomes.
 
For both arms, the patients must be screened at Duke within 3 ± 1 weeks after the completion of standard of care radiation. For both arms, the initial cycle of adjuvant TMZ will begin as soon as possible following randomization. For Arm 1, the adjuvant TMZ cycle(s) will be given at a standard targeted dose of 150-200 mg/m²/d for 5 days. For Arm 2, the adjuvant TMZ cycle(s) will be at the dose-intensified dose of 75-100 mg/m²/d for 21 days. If a patient enrolls after approval of protocol version 20181218 and has an MGMT unmethylated tumor, they will discontinue TMZ after the 1st cycle.
 
All patients will have blood drawn for immune monitoring and then receive a tetanus pre-conditioning injection intradermally (i.d.) in the RIGHT groin (as described below) on day 22 (+1 day) of cycle 1 of adjuvant TMZ. On the following day, the patients will receive study vaccine. The vaccine is administered as follows: 500 µg of PEP-CMV Component A mixed with Montanide ISA-51 administered i.d. with half on the right groin and half on the left groin. Vaccines #2 and #3 will be given at 2 week (+ 3 days) intervals; the MRI visit with immune monitoring will take place within 2 weeks (+3 days) of vaccine #3. Prior to the 20181218 amendment, vaccination consisted of two components: Component A and Component B. However, after that amendment, vaccination for all newly enrolled patients consisted of Component A only.
 
For patients enrolled before approval of protocol version 20181218 and for patients enrolled after approval of protocol version 20181218 who have an MGMT methylated tumor or MGMT methylation status in inconclusive, TMZ cycle 2 will begin after that visit, but no sooner than 14 days post vaccine 3. This will result in at least ~35-day delay before starting TMZ cycle 2. MGMT unmethylated patients enrolled after approval of protocol version 20181218 will not receive subsequent cycles of TMZ, but will continue to receive vaccines approximately every 4 (+2) weeks.
 
An unacceptable toxicity will be defined as any \geq Grade 3 toxicity possibly, probably, or definitely related to the PEP-CMV vaccine with the following exceptions. A portion of the Grade 3 vaccine reactions noted in prior patient experiences with the PEP-CMV vaccine, described in Sections 11.5.1 and 14.2.1, will not be considered unacceptable if they are indicative of immune response. That is, toxicities such as Grade 3 flu-like symptoms, fever, and chills/rigors will not be considered unacceptable toxicities if the duration is less than 72 hours. Any \geq Grade 3 organ toxicity (cardiac, renal, hepatic), including CRS-related toxicities such as hypotension and

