--	---

	
tachycardia, of any duration will be considered an unacceptable toxicity. Although not considered an unacceptable toxicity, any patient with \geq Grade 2 urticaria will not receive further vaccines, will be withdrawn from the study, and will be replaced if less than 3 vaccines have been administered without unacceptable toxicity. The prevalence of unacceptable toxicities occurring during the initial 3 bi-weekly vaccinations or the vaccinations administered concurrently with temozolomide will be continuously monitored. If more than 25% of accrued patients experience unacceptable toxicities, then accrual will be suspended and reported toxicity will be carefully reviewed to determine if modifications to the protocol treatment should occur. Peptide vaccinations employing Montanide ISA-51 as adjuvants have generally been well-tolerated in human patients in numerous phase I-III trials.
 
Treatment Plan: Patients will be vaccinated in conjunction with subsequent 28-day cycles for a total of 6 to 12 adjuvant TMZ cycles after RT if patient is continuing on TMZ (i.e., for patient's who's tumor is methylated or the status is inconclusive). Cycles are every 4 (+ 2) weeks, adjusting for slight delays on startup or scheduling of each 28-day cycle. For patients whose tumor is methylated or the status is inconclusive, the total number of TMZ cycles given will be at the discretion of the treating oncologist. During the 28-day cycles, vaccinations will occur on day 23 (-1 day, + 2 days) of each cycle for each arm: (Arm 1) standard TMZ (200 mg/m²/day on days 1-5 of each 28-day cycle), or (Arm 2) dose-intensified TMZ (100 mg/m²/day on days 1-21 of each 28-day cycle).
 
All vaccines will be given i.d. approximately 10 cm below the inguinal ligament bilaterally. Component A will be administered half in the RIGHT groin and half in the LEFT groin at a maximum of 0.2 mL per intradermal injection. A target of six cycles with maximum of twelve cycles of TMZ may be given to patients enrolled before approval of protocol version 20181218 and to methylated patients enrolled after approval of protocol version 20181218, at the discretion of the treating neuro-oncologist. Unmethylated patients enrolled after approval of protocol version 20181218 will receive only one cycle of TMZ. After the completion of a patient's last TMZ cycle, vaccines will continue every 4-6 weeks for a maximum number of 20 vaccines (unless tumor progression occurs).
 
Patients will be imaged with contrast-enhanced MRI within 2 weeks (+3 days) after vaccine 3 and then approximately every 8 weeks [every 2 cycles thereafter (i.e., end of cycles 3, 5, 7, 9, 11)]. RANO criteria will be used for assessment of pseudo-progression, and patients demonstrating definitive progression will be removed from study. Any patient removed prior to immune monitoring post vaccine 3 will be replaced for immunologic endpoints. Clinical endpoint comparisons will be made amongst patients successfully randomized to adjuvant TMZ treatment arms and receiving at least one vaccine.
 
Blood for immune monitoring will be obtained:
 
• Prior to Td pre-conditioning• During vaccines 1 and 2 (just prior to Component A, 1 and 2 hours after Component A)• Prior to vaccine 3• After vaccine 3 (within 2 weeks of vaccine 3 [+ 3 days])• Prior to vaccines 4 and 6

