15.4 Analytic Methods

15.4.1 Primary Analyses

Safety: To assess the safety of PEP-CMV vaccination in combination with adjuvant TMZ, the percentage of patients with unacceptable toxicity will be estimated within each arm. All patients who received any PEP-CMV vaccine will be included in these safety analyses.

As described in Section 15.1, the vaccination treatment regimen has been modified over time due to safety issues. Hence, toxicity will be summarized for each period of study conduct as follows:

- Initial randomization period where patients were assigned to one of two TMZ regimens with both Component A and B. The 2 patients assigned to standard TMZ after randomization resumed who received both Component A and B will also be included in this summary.
- Safety Cohort Period in which all patients received standard TMZ with vaccine Component A and B
- Randomization period in which patients received at least one cycle of Component B prior to discontinuation
- Randomization period in which patients are assigned to one of two TMZ regimens and receive only vaccine Component A

Immunologic Response: The primary analysis will focus on patients who have follow-up immunologic monitoring after the 3rd vaccination and before initiation of the second TMZ/vaccine cycle. Such a patient is considered “evaluable” for the immunologic response primary analyses.

The Wilcoxon rank sum test will compare treatment groups with regard to the median peak number of T cells that secrete IFNy by ELISPOT in response to component A of PEP-CMV. Analyses will include only those patients who have an assessment of immune response after receiving 3 vaccinations.

Though the original vaccination included Component A and B, the primary immunologic analysis will focus on only those patients who received Component A alone. Additional exploratory analyses may include data from the few “evaluable” patients who received both vaccine Components A and B.

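### The Synopsis and Section 11.5.4 define unacceptable toxicity differently: Section 11.5.4 adds a life-threatening condition that the Synopsis does not have

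*Combined protocol and SAP*

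**What the plan says.** The Synopsis (Study Design) counts any ≥ "Grade 3 toxicity possibly, probably, or definitely related to the PEP-CMV vaccine with the following exceptions". Section 11.5.4 first gives the superseded definition, labelled as the original one, and then the current one: "The definition of unacceptable toxicity was revised with v.20200117 of the protocol and will be defined now as any life-threatening" ≥ Grade 3 toxicity, with the same three levels of relatedness and again with exceptions.

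The rest of the definition is the same in both places. Under the exemption, "toxicities such as Grade 3 flu-like symptoms, fever, and chills/rigors will not be considered unacceptable toxicities if the duration is less than 72 hours". Under the organ clause, any cardiac, renal or hepatic toxicity of Grade 3 or higher, "including CRS-related toxicities such as hypotension and tachycardia, of any duration will be considered an unacceptable toxicity".

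Three things depend on the term:

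- Treatment (Section 11.5.4): "Patients who experience unacceptable toxicities will not continue to receive vaccine therapy".
- Accrual (Synopsis, repeated in Section 11.5.4 and, with slightly different wording, in Section 15.3): "If more than 25% of accrued patients experience unacceptable toxicities, then accrual will be suspended and reported toxicity will be carefully reviewed".
- Primary safety analysis (Section 15.4.1): "the percentage of patients with unacceptable toxicity will be estimated within each arm", in all patients who received any PEP-CMV vaccine.

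Section 15.3 refers to Section 11.5.3 for the definition, describes it as the one modified in v.20200117, and reports that no patient had met it as of that amendment. Section 11.5.3 is now Allergy Testing.

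**The concern.** A primary endpoint needs one definition, and so does a rule that suspends accrual. Here two current texts give two, and nothing in the protocol says which governs. Two people scoring the same adverse event record could report different safety percentages for an arm, and could disagree on whether a patient may have another dose or whether accrual should pause. The trial has already had several safety events and changes of regimen, so the scoring of Grade 3 vaccine reactions is a practical matter.

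**Working it through.** The plan states no figure for this point, so there is none to reproduce. The check is a comparison of the two texts, followed by one piece of arithmetic on scale.

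**Step 1: are both texts current?** Yes. Section 11.5.4 sets the superseded wording apart as the original definition and introduces the other as how the term is defined now. Its note about an update in v.20200504 follows the word for exceptions, so it does not clearly remove the qualifier.

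**Step 2: where do they differ?** All events below are taken to be at least possibly related to the vaccine.

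| Event | Synopsis | Section 11.5.4, read literally |
|---|---|---|
| Grade 3 flu-like symptoms, fever or chills/rigors, under 72 hours | Not counted | Not counted |
| Grade 3 or higher cardiac, renal, hepatic or CRS-related toxicity, any duration | Counted | Counted |
| Other life-threatening Grade 3 or higher event, not exempt | Counted | Counted |
| Grade 3 fever or flu-like symptoms, 72 hours or more, not life-threatening | Counted | Not counted |
| Grade 3 lactic acidosis, not life-threatening | Counted, unless read as an exempt immune reaction | Not counted, unless read as organ/CRS toxicity |

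The fourth row is the plain case. The fifth is only a possible one. Section 14.2.1 records Grade 3 lactic acidosis, but the exemption and the CRS clause both use open-ended lists, so its class depends on how they are read. Urticaria is handled the same way in both texts.

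**Step 3: which wording fits the rest of the definition?** The 72-hour exemption removes short Grade 3 fever, chills and flu-like symptoms. If only life-threatening events counted in the first place, there would be little for it to remove. The organ/CRS clause counts Grade 3 events with no life-threatening condition. Both fit the Synopsis wording better. The amendment log for 20200826 lists Sections 1 and 11.5.4 together for the revision of this definition, which suggests that they were meant to agree. The log is used here for that purpose only.

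**Step 4: scale.** The number of events in the gap is not in the documents. For illustration, take the 15 patients who had received only Component A as of 20200110 (Section 15.1).

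- One patient: 1/15 = 6.7 percentage points.
- Smallest count above 25%: 0.25 × 15 = 3.75, so 4 patients are needed. 3/15 = 20.0% does not trip the rule; 4/15 = 26.7% does.

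The choice of 15 is an assumption, because the plan does not say which patients make up the accrued denominator.

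**The case against.** The best case on the other side is that Section 11.5.4, read as a whole, already counts the 72-hour event: an exemption limited to under 72 hours implies that longer events are covered. That is a fair reading, but it works only by giving the qualifier no effect. It supports deleting the word and does not remove the conflict.

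The second argument is that the gap is narrow and other safeguards exist, and this stands. Organ toxicity, CRS hypotension and tachycardia count under both texts. Section 11.10.1 lets the investigator withdraw a patient, Section 14.3 calls for action on an unexpected frequency of grade III or IV events, and Section 11.5.5 keeps a summary of all adverse events by grade and relationship, so either definition can be tabulated later. The safety analysis is an estimate with no test attached, and crossing 25% leads to a review, not to closure. None of this settles which events enter the endpoint or the rule, but it limits the severity.

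The third argument is that the wording agreed with the FDA is not available to us. This also stands, and the fix allows for it.

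A reader might go further in three ways that the documents do not support.

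- That the zero in Section 15.3 is false because Section 14.2.1 records Grade 3 hypotension. The statement is dated and refers to the v.20200117 definition. Nothing shows that it was wrong when written.
- That one extra event among 13 per arm would lift the upper confidence limit above the 25% level. Thirteen per arm is the target for immune-evaluable patients, whereas safety covers all vaccinated patients, and the rule uses the observed share.
- That the qualifier disables the suspension rule. A single patient separates continuing from suspending only if three of the 15 already count, and no such count is shown.

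**Conclusion.** The inconsistency is real and lies in current text. For related, non-life-threatening Grade 3 events that are neither exempt nor organ/CRS toxicity, the vaccine stop, the primary safety percentage per arm and the accrual suspension depend on which section is followed. The Synopsis wording is the better supported of the two, because the added qualifier sits badly with the rest of Section 11.5.4.

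The effect on results is unknown, since the documents do not show how many events fall in the gap. The figure of 6.7 points per patient rests on taking the 15 Component A-only patients as the denominator and says nothing about what has occurred. This should be fixed, but it does not undermine the design: no test, power or sample size depends on it.

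**What to change.** - Delete the life-threatening qualifier from Section 11.5.4 so that it matches the Synopsis, after confirming this against the definition agreed under the IND. If the agreed definition does contain the qualifier, change the Synopsis and reconcile the 72-hour and organ/CRS clauses with it.
- Use that one definition in Section 15.3 and correct its cross-reference from 11.5.3 to 11.5.4.
- State whether Grade 3 lactic acidosis is exempt.
- Score all recorded related Grade 3 or higher events, in all vaccinated patients, against the single definition for Section 15.4.1 and the 25% rule. Do not carry forward the zero in Section 15.3; give a dated count instead.

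The cost is one word, one updated paragraph and the re-adjudication of a few events already collected. The safety record may look less favourable afterwards.
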